Amendment number	Date	Protocol section(s) changed	Summary of amendment(s)	Reason
			characteristic/exposure”	
			The “Role” of the following variables is simplified to “Baseline characteristic” while the terms “Potential confounder” and/or “Risk factor” are removed from the “Role”: age (continuous), age (categorical), gender, race, ethnicity, region, insurance, BMI, smoking, hypertension, hyperlipidemia, coronary artery disease, history of serious infections, malignancy, pregnancy, interstitial lung disease/COPD/Asthma, venous thromboembolism, heart disease, history of cerebrovascular accident, peripheral vascular disease, other immune deficiencies, HIV/AIDS, diabetes, chronic kidney disease/dialysis, liver disease, and corticosteroid use.	None of these variables was described elsewhere in the protocol or in the SAP as a potential confounder or risk factor, and they were not analyzed as potential confounders or risk factors.
			The “Role” of influenza-like illness is changed from “Endpoint” to “Primary Endpoint.”	The SAP and elsewhere in the protocol clearly indicate that influenza-like illness is a primary endpoint, which is the term used in the protocol to describe the role of the study’s other primary endpoint, influenza.
			The “Role” of influenza vaccine is changed from “Potential Confounder” to “Secondary Endpoint.”	Influenza vaccine was not described elsewhere in the protocol or in the SAP as a potential confounder, and it was not analyzed as a potential confounder. In both documents, it is stated that influenza

RedactedRedacted
RedactedRedactedRedactedRedactedRedactedRedactedRedactedRedactedRedacted
Redacted
Redacted

Amendment number	Date	Protocol section(s) changed	Summary of amendment(s)	Reason
				vaccination will be “reported” for each influenza season, with no additional elaboration.
			The “Role” of the following variables is changed from either “Endpoint/Complication” or “Endpoint” to “Secondary Endpoint”: Influenza complication - pneumonia, Influenza complication - stroke or myocardial infarction, Influenza complication - neurological disorder, corticosteroid use, methotrexate use, azathioprine use, influenza hospitalization, in-hospital death, and death.	The SAP and elsewhere in the protocol clearly indicate these variables are secondary endpoints – the other terms used to describe their roles in the protocol are superfluous or under-specified.
		Section 5	Updated Study Report Date	Administrative

RedactedRedacted
RedactedRedactedRedactedRedactedRedactedRedactedRedactedRedacted
Redacted
Redacted

Additionally, the frequencies and incidence rates of influenza infection and influenza like illness, and the frequencies of influenza-related clinical outcomes, including mortality, will be reported by influenza season (annual datacut from 01 June – 31 May). Although there may be under-reporting and misclassification, presence of influenza vaccine in individual patient records will also be reported for each influenza season.

8. RESEARCH METHODS

8.1. Study Design

This is a retrospective records-based cohort study involving secondary analysis of **Redacted** Electronic Health Record (EHR) databases in the US consisting of longitudinal health information about patients derived from participating healthcare provider organizations with details below.

This study period is 01 June 2014 through 31 May 2019. The June 2014 start date is intended to avoid potentially intractable channeling of patients with high unmet need into tofacitinib group given status as first in class to a new mechanism of action following US approval in November 2012.

This study first focuses on the whole study period (01 June 2014 through 31 May 2019), then perform frequency and incidence rate analysis for each influenza season (01 June through 31 May the next year).

8.2. Setting

8.2.1. **Redacted**

Redacted is derived from records of 150,000 healthcare providers in the United States, that include more than 2000 hospitals and 7000 clinics; treating more than 103 million patients receiving care as of January 2020. The data is certified as de-identified by an independent statistical expert following Health Insurance Portability and Accountability Act (HIPAA) statistical de-identification rules, and managed according to **Redacted** customer data use agreements.^{18,19} Clinical, claims and other medical administrative data is obtained from both Inpatient and Ambulatory EHRs, practice management systems and numerous other internal systems. Information is processed, normalized, and standardized across the continuum of care from both acute inpatient stays and outpatient visits. **Redacted** data elements include: demographics, medications prescribed and administered, immunizations, allergies, lab results (including microbiology), vital signs and other observable measurements, clinical and inpatient stay administrative data and coded diagnoses and procedures. In addition, **Redacted** uses natural language processing (NLP) computing technology to transform critical facts from physician notes into usable datasets. The NLP data provides detailed information regarding signs and symptoms, family history, disease related scores (ie, RAPID3 for RA, or CHADS2 for stroke risk), genetic testing, medication changes, and physician rationale behind prescribing decisions that might never be recorded in the EHR.

RedactedRedacted
RedactedRedactedRedactedRedactedRedactedRedactedRedactedRedacted
Redacted
Redacted

8.2.3. Inclusion Criteria

In order to be eligible for entry into an indicated patient cohort patients must meet all of the following inclusion criteria:

1. Aged ≥ 18 years at index date
2. Evidence of at least 1 inpatient diagnosis code or 2 outpatient diagnosis codes 7-365 days apart for RA, PsA, or UC.
3. Evidence of initiation for at least 1 approved systemic treatment (tofacitinib, JAKi, TNFi, non-TNFi, csDMARD) for the corresponding identified indication.
4. At least 180 days of continuous enrollment in **Redacted** prior to index date.

8.2.4. Exclusion Criteria

Patients will be excluded if they meet any of the following criteria:

1. Evidence of >1 indications of interest during the whole study period.

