8.3. Variables

All variable definitions will be specifically defined in the SAP, including code lists, time periods of interest and data location.

Variable	Role	Operational definition ^a
Rheumatoid Arthritis	Subcohort identification	At least 1 inpatient or 2 outpatient diagnoses 7-365 days apart
Psoriatic Arthritis	Subcohort identification	At least 1 inpatient or 2 outpatient diagnoses 7-365 days apart
Ulcerative Colitis	Subcohort identification	At least 1 inpatient or 2 outpatient diagnoses 7-365 days apart
Index date	Baseline characteristic	Date of initiation of index therapy
Baseline systemic therapy	Baseline Characteristic/Exposure	Evidence of therapy prescribed 180 days prior to index date. Categorical: , tofacitinib, JAKi, TNFi, non-TNFi, csDMARD
Baseline tofacitinib	Baseline Characteristic/Exposure	Evidence of tofacitinib prescribed within 180 days prior to index date.
Baseline JAKi	Baseline Characteristic/Exposure	Evidence of JAKi prescribed within 180 days prior to index date.
Baseline TNFi	Baseline Characteristic/Exposure	Evidence of TNFi prescribed within 180 days prior to index date.
Baseline Non-TNFi	Baseline Characteristic/Exposure	Evidence of Non-TNFi prescribed within 180 days prior to index date.

RedactedRedacted
RedactedRedactedRedactedRedactedRedactedRedactedRedactedRedactedRedacted
Redacted
Redacted

Variable	Role	Operational definition ^a
Baseline csDMARD	Baseline Characteristic/Exposure	Evidence of csDMARD prescribed within 180 days prior to index date.
Age, continuous	Baseline Characteristic	Continuous age at index date
Age, categorical	Baseline Characteristic	Age at index date: 18-24, 25-34, 35-44, 45-54, 55-64, 65-74, 75-84, 85+
Age, dichotomous	Stratifying variable	18-64 and ≥ 65
Gender	Baseline Characteristic	Female, Male, Unknown
Race	Baseline Characteristic	White, Black, Asian, Other
Ethnicity	Baseline Characteristic	Hispanic, non-Hispanic
Region	Baseline Characteristic	Distribution of geographic region at index date
Insurance	Baseline Characteristic	Insurance type
BMI	Baseline Characteristic	BMI<30 and BMI ≥ 30
Smoking	Baseline Characteristic	Current/former/non-smoker
Hypertension	Baseline Characteristic	Diagnosis of hypertension within baseline period
Hyperlipidemia	Baseline Characteristic	Diagnosis of hyperlipidemia within baseline period
Coronary artery disease	Baseline Characteristic	Diagnosis of coronary artery disease within baseline period

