8.7. Data Analysis

Detailed methodology will be documented in a SAP, which will be dated, filed and maintained by the sponsor. The SAP may modify the plans outlined in the protocol; any major modifications of primary endpoint definitions or their analyses would be reflected in a protocol amendment. Descriptive analysis will be performed for this study. Baseline demographics, comorbidities and clinical characteristics will be analyzed using baseline data for RA, PsA and UC patients, then stratified by index treatment group, and age (<65 and 65 and older). Means, medians, and standard deviations will be provided for continuous variables. Counts and percentages will be provided for dichotomous variables or categorical variables.

RedactedRedacted
RedactedRedactedRedactedRedactedRedactedRedactedRedactedRedacted
Redacted
Redacted

The frequency and incidence rates for influenza and influenza like illness, the frequency of influenza complications, influenza-related hospitalization and mortality among patients treated for RA, PsA, and UC in subsets of patients defined by different index treatments will be reported stratified by age (<65 and 65 and older).

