8.9. Limitations of the Research Methods

The **Redacted** is large and covers a wide geographic area; however, limitations that are general to all claims database analyses as well as those specific to this study should be noted. Diagnosis of autoimmune conditions will be identified using ICD-10-CM diagnosis codes, which are subject to potential miscoding, though presumably without respect to the treatment or outcomes. Where possible, validated algorithms will be used. The baseline period of this study is of limited duration thus baseline comorbidities and risk factors occurring outside of this baseline period may not be captured, which may lead to misclassification.

Information on prescriptions for outpatients does not necessarily indicate that the medication was consumed or taken as prescribed; similarly, medications filled over-the-counter or provided as samples by the physician will not be recorded in the database. Although information on vaccinations will be collected if contained in the database; this is likely to be under-reported as many vaccinations are given at alternative locations; however, this is not likely to be differential.

Cases not requiring treatment or office visits tend to be systematically under-recorded in such databases; therefore, it is possible that this study will only capture severe manifestations of such disorders; this may be particularly true for ILI.

The primary analyses are descriptive in nature and inferences regarding association of treatment or indication are not possible. Feasibility of comparative analyses will depend on the number of infected patients with indications/treatments of interest.

Study results may not be generalizable outside of the insured population.

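### Excluding patients for a second indication coded at any time in the study period makes cohort entry depend on post-index information, which may bias the influenza and ILI rates by an unknown amount

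*Supplement*

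**What the plan says.** Section 8.2.4 has one exclusion criterion: "Evidence of >1 indications of interest during the whole study period". Section 8.1 fixes that window: "This study period is 01 June 2014 through 31 May 2019". Section 8.3 defines index as "Date of initiation of index therapy", so it falls on a different day for each patient.

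Section 8.2.3 admits a patient on "Evidence of at least 1 inpatient diagnosis code or 2 outpatient diagnosis codes 7-365 days apart for RA, PsA, or UC", and Section 8.3 uses the same algorithm to define each of the three indications. The comorbidities in Section 8.3 are confined to the baseline period. The second-indication rule is not.

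Section 8.7 makes "The frequency and incidence rates for influenza and influenza like illness" a main output, by indication, index treatment and age. Sections 8.1 and 8.3 add a breakdown into five annual influenza seasons.

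The text shown has no censoring rule for a later second indication and no sensitivity analysis of this criterion. The limitations in Section 8.9 do not mention it.

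**The concern.** A cohort should be defined by what is known when follow-up begins. Here a patient who starts RA therapy in 2014 and meets the PsA definition in 2018 is removed retroactively, with four years of person-time and any influenza recorded in it. The rates then describe people known with hindsight never to have acquired a second indication.

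Two consequences follow.

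- **Removal depends on the time left to observe.** Someone indexed in the first year has up to five years in which to be excluded; someone indexed in the last year has at most one. The selection therefore differs by index year. It can differ by season, and by treatment group if groups start at different calendar times.
- **Removal may be related to the outcome.** A second code needs visits, and so does an influenza code. Section 8.9 concedes the latter: "Cases not requiring treatment or office visits tend to be systematically under-recorded in such databases". If frequent attenders are removed more often, the retained patients have a lower recorded rate.

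**Working it through.** The documents give no excluded share, coding rate or influenza rate, so there is no figure of the plan to reproduce. The dates and definitions come from Sections 8.1 to 8.3. **Every numerical input below other than the five-year period is an assumption.**

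**1. Timing.** The exclusion window ends on 31 May 2019 for everyone, while index varies. The post-index part of the window is 31 May 2019 minus the index date, or the patient's last record if earlier. It is positive for almost every patient and at most about five years.

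**2. Share removed by post-index codes.** With second-indication hazard h per year and t years from index to study end, the share is 1 - exp(-h t). For h = 0.03:

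- indexed mid-year 1 (t = 4.5): 1 - exp(-0.135) = 12.6%
- indexed mid-year 5 (t = 0.5): 1 - exp(-0.015) = 1.5%

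This is a share of patients, not an error in a rate.

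**3. From share removed to rate bias.** Let q be the share of person-time removed and r the influenza rate in removed patients relative to retained ones. If the retained rate is L, the full-cohort rate is L[(1 - q) + q r]. Hence retained/full = 1/[(1 - q) + q r].

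| q | r = 0.8 | r = 1 | r = 1.5 | r = 2 | r = 3 |
|---|---|---|---|---|---|
| 1% | +0.2% | 0 | -0.5% | -1.0% | -2.0% |
| 5% | +1.0% | 0 | -2.4% | -4.8% | -9.1% |
| 10% | +2.0% | 0 | -4.8% | -9.1% | -16.7% |

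Example: q = 5%, r = 2 gives 1/(0.95 + 0.10) = 0.952, or -4.8%. With r = 1 there is no bias, whatever the share removed.

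**4. Simulation.** It used 2,000,000 patients, index uniform over five years, follow-up to study end, and an influenza rate of 0.02 per person-year. A gamma contact factor (mean 1, variance v) multiplies both the influenza rate and the second-code hazard h.

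| v | h | Patients removed | Rate bias, all | Removed, index year 1 / 5 | Bias, index year 1 / 5 |
|---|---|---|---|---|---|
| 0 | 0.01 | 2.5% | +0.1% | 4.4% / 0.5% | +0.3% / +0.1% |
| 0 | 0.03 | 7.2% | -0.1% | 12.7% / 1.5% | +0.1% / 0.0% |
| 0.5 | 0.01 | 2.4% | -1.6% | 4.4% / 0.5% | -2.1% / -0.4% |
| 0.5 | 0.03 | 7.0% | -4.7% | 12.2% / 1.5% | -6.2% / -1.3% |
| 1 | 0.01 | 2.4% | -3.3% | 4.3% / 0.5% | -4.4% / -0.5% |
| 1 | 0.03 | 6.8% | -9.0% | 11.9% / 1.4% | -12.0% / -1.6% |

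The v = 0 rows differ from zero only by simulation error. A hand check supports the last row. Under this model, patients retained over u years have a relative rate of 1/(1 + v h u). The person-time-weighted mean of u is 10/3 years, so the bias is about 1/(1 + 0.03 × 10/3) - 1 = -9.1%.

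**5. Effect of the fix in the same model.** If the exclusion uses only data up to index and follow-up is kept, this bias is 0. If follow-up is censored at the second indication, the mean time since index of the person-time is about 5/3 years. In the strongest scenario the rate is then about 1/(1 + 0.03 × 5/3) - 1 = -4.8% against full follow-up, roughly half the departure under the present rule. Censoring uses no future information, but it is not neutral if it is related to contact. The censored rate describes time lived with one indication to date.

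**The case against.** The strongest defence is that single-indication cohorts are a legitimate aim, and that a later, different diagnosis may show the first label was wrong. Excluding such patients buys a cleaner cohort. That stands as a reason to keep the whole-period rule as a sensitivity analysis, but not as a reason to let it decide entry to the main cohort unreported.

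The study is also descriptive, and Section 8.9 disclaims inference about treatment or indication. No planned comparison is therefore undermined, which limits the severity. A descriptive rate still needs a population defined at the start of follow-up.

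No SAP is shown, nor Section 8.2.2, and Section 8.3 leaves code lists and time periods to the SAP. The start of time at risk is not stated in the text shown; index is the natural reading, and its absence is no finding. For this criterion, though, the protocol states the window itself.

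Section 8.9 calls the diagnosis codes "subject to potential miscoding, though presumably without respect to the treatment or outcomes". If that also held for second-indication codes, the bias would be near zero. It is a presumption, however, and sits uneasily with the admission that recording depends on contact.

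Four stronger readings are tempting but not supported:

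- **The rates are biased.** Events and person-time are removed together, so the rate moves only if removed patients have a different rate. The documents do not say whether they do.
- **The share excluded is the error.** In the simulation, 7.2% of patients are removed with essentially no bias when second coding is unrelated to influenza.
- **One rule-out code excludes.** Both criteria speak of evidence, and Section 8.3 defines each indication by the one-inpatient or two-outpatient algorithm. The natural reading is that a patient must meet two such definitions.
- **Time between qualifying codes is immortal.** Influenza or ILI can be diagnosed in that interval and the patient still qualifies. Only death or loss before the second code is ruled out, and only where the codes are not complete by index, a timing the SAP may settle.

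**Conclusion.** The point holds in limited form. Section 8.2.4 conditions cohort entry on information recorded after index, and nothing shown limits or offsets this. Removal is more frequent for early-index patients: about 12-13% of those indexed in year 1 against about 1.5% in year 5, at an assumed 3% per year.

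The resulting rates may be biased overall, by season and by index treatment. Downward is the likelier direction, because both kinds of code need health-care contact; it would be upward if removed patients had the lower rate. The simulated overall bias is about 0 under independence and -1.6% to -9.0% with shared contact intensity. These figures rest on assumed hazards of 1-3% per year, assumed contact variances of 0.5-1 and follow-up to study end. They show what is possible and do not estimate the bias in this study.

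This is a cheap improvement to the design. The documents do not support treating it as a defect that invalidates the results.

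**What to change.** 1. In Section 8.2.4, apply the exclusion using records on or before the index date only, with the same one-inpatient or two-outpatient definition as inclusion. Use all available history up to index: two outpatient codes may lie up to 365 days apart, while the guaranteed look-back is 180 days ("At least 180 days of continuous enrollment in" the database before index).
2. Censor on the date a later second indication meets that definition. For a pair of outpatient codes, this is the date of the second.
3. Keep the whole-period exclusion as a sensitivity analysis.
4. Report the number of patients excluded solely for post-index codes, ideally by index year and index treatment. This is the figure needed to judge whether the issue matters.
5. Because censoring may itself be related to contact, it would help to give the rates once more with follow-up kept after the second indication.
6. Add a sentence on this criterion to Section 8.9.

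**Cost.** A wording change, a re-run of cohort selection and a few extra table rows on data already held in structured form; no new data collection. The downside is that a few patients whose first diagnosis label was wrong stay in that cohort until censored. The sensitivity analysis shows how far that affects the rates.

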8.3. Variables

All variable definitions will be specifically defined in the SAP, including code lists, time periods of interest and data location.

Variable	Role	Operational definition ^a
Rheumatoid Arthritis	Subcohort identification	At least 1 inpatient or 2 outpatient diagnoses 7-365 days apart
Psoriatic Arthritis	Subcohort identification	At least 1 inpatient or 2 outpatient diagnoses 7-365 days apart
Ulcerative Colitis	Subcohort identification	At least 1 inpatient or 2 outpatient diagnoses 7-365 days apart
Index date	Baseline characteristic	Date of initiation of index therapy
Baseline systemic therapy	Baseline Characteristic/Exposure	Evidence of therapy prescribed 180 days prior to index date. Categorical: , tofacitinib, JAKi, TNFi, non-TNFi, csDMARD
Baseline tofacitinib	Baseline Characteristic/Exposure	Evidence of tofacitinib prescribed within 180 days prior to index date.
Baseline JAKi	Baseline Characteristic/Exposure	Evidence of JAKi prescribed within 180 days prior to index date.
Baseline TNFi	Baseline Characteristic/Exposure	Evidence of TNFi prescribed within 180 days prior to index date.
Baseline Non-TNFi	Baseline Characteristic/Exposure	Evidence of Non-TNFi prescribed within 180 days prior to index date.

RedactedRedacted
RedactedRedactedRedactedRedactedRedactedRedactedRedactedRedactedRedacted
Redacted
Redacted

Variable	Role	Operational definition ^a
Baseline csDMARD	Baseline Characteristic/Exposure	Evidence of csDMARD prescribed within 180 days prior to index date.
Age, continuous	Baseline Characteristic	Continuous age at index date
Age, categorical	Baseline Characteristic	Age at index date: 18-24, 25-34, 35-44, 45-54, 55-64, 65-74, 75-84, 85+
Age, dichotomous	Stratifying variable	18-64 and ≥ 65
Gender	Baseline Characteristic	Female, Male, Unknown
Race	Baseline Characteristic	White, Black, Asian, Other
Ethnicity	Baseline Characteristic	Hispanic, non-Hispanic
Region	Baseline Characteristic	Distribution of geographic region at index date
Insurance	Baseline Characteristic	Insurance type
BMI	Baseline Characteristic	BMI<30 and BMI ≥ 30
Smoking	Baseline Characteristic	Current/former/non-smoker
Hypertension	Baseline Characteristic	Diagnosis of hypertension within baseline period
Hyperlipidemia	Baseline Characteristic	Diagnosis of hyperlipidemia within baseline period
Coronary artery disease	Baseline Characteristic	Diagnosis of coronary artery disease within baseline period
History of serious infections	Baseline Characteristic	Hospitalized infections within baseline period
Malignancy	Baseline Characteristic	Diagnosis of malignancy within baseline period
Pregnancy	Baseline C haracteristic	Diagnosis of pregnancy within baseline period
Interstitial lung disease (ILD)/COPD/Asthma	Baseline Characteristic	Diagnosis of ILD/COPD/Asthma within baseline period
Venous thromboembolism (VTE)	Baseline Characteristic	Diagnosis of pulmonary embolism (PE) or deep vein thrombosis (DVT) within baseline period
Heart disease (HD)	Baseline Characteristic	Diagnosis of HD (heart failure, hypertensive heart disease, pulmonary heart disease, valvular disorders, arrhythmia, congenital

RedactedRedacted
RedactedRedactedRedactedRedactedRedactedRedactedRedactedRedactedRedacted
Redacted
Redacted

Variable	Role	Operational definition ^a
		heart disease) within baseline period
History of cerebrovascular accident (CVA)	Baseline Characteristic	History of ischemic or hemorrhagic stroke within baseline period
Peripheral vascular disease (PVD)	Baseline Characteristic	Diagnosis of PVD within baseline period
Other immune deficiencies	Baseline Characteristic	Diagnosis of immunodeficiency within baseline period
Human immunodeficiency virus (HIV)/AIDS	Baseline Characteristic	Diagnosis of HIV/AIDS within baseline period
Diabetes	Baseline Characteristic	Diagnosis of diabetes within baseline period
Chronic kidney disease (CKD)/Dialysis	Baseline Characteristic	Diagnosis of CKD or dialysis procedure during baseline period
Liver Disease	Baseline Characteristic	Diagnosis or procedure during baseline period
Corticosteroid Use	Baseline Characteristic	Prescription during baseline period for systemic corticosteroids
Influenza Season	Stratifying variable	Annually June 1 st – May 31 st 2014-2015; 2015-2016; 2016-2017; 2017-2018; 2018-2019
Influenza	Primary Endpoint	Clinical diagnosis of influenza
ILI	Primary Endpoint	Clinical diagnosis of ILI
Influenza vaccine	Secondary Endpoint	Yes/No, evidence of influenza vaccine corresponding to seasons: 2014-2015; 2015-2016; 2016-2017; 2017-2018; 2018-2019 This will only be reported for each influenza season
Influenza Complications - Pneumonia	Secondary Endpoint	Clinical diagnosis of pneumonia on or up to 30 days after an influenza diagnosis
Influenza Complications - Stroke or myocardial infarction (MI)	Secondary Endpoint	Clinical diagnosis of stroke or MI on or up to 30 days after an influenza diagnosis
Influenza Complications – Neurological Disorder	Secondary Endpoint	Clinical diagnosis of neurological disorder on or up to 30 days after an influenza diagnosis

RedactedRedacted
RedactedRedactedRedactedRedactedRedactedRedactedRedactedRedactedRedacted
Redacted
Redacted

Variable	Role	Operational definition ^a
Corticosteroid Use	Secondary Endpoint	Corticosteroid use within 30 days [-30,30] around an influenza diagnosis
Methotrexate Use	Secondary Endpoint	Methotrexate use within 30 days [-30,30] around an influenza diagnosis
Azathioprine Use	Secondary Endpoint	Azathioprine use within 30 days [-30,30] around an influenza diagnosis
Influenza Hospitalization	Secondary Endpoint	Yes/No: hospitalization within 30 days post influenza diagnosis
In-hospital death	Secondary Endpoint	Death that happened during influenza hospitalization
Death	Secondary Endpoint	Death within 90 days post influenza diagnosis

a. Where applicable codes and other definitions to be further defined in the SAP.

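### Corticosteroid, methotrexate and azathioprine use is counted in one window spanning the influenza diagnosis, so use before infection cannot be separated from use after it

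*Supplement*

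**What the plan says.** The variable table in Section 8.3 lists three drug-use variables as secondary endpoints, each with a window on both sides of the diagnosis:

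- Corticosteroids: "Corticosteroid use within 30 days [-30,30] around an influenza diagnosis"
- Methotrexate: "Methotrexate use within 30 days [-30,30] around an influenza diagnosis"
- Azathioprine: "Azathioprine use within 30 days [-30,30] around an influenza diagnosis"

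The clinical outcomes in the same table look forward only. Pneumonia is "Clinical diagnosis of pneumonia on or up to 30 days after an influenza diagnosis", and hospitalization is "Yes/No: hospitalization within 30 days post influenza diagnosis". Stroke or MI, neurological disorder and death are likewise counted from the diagnosis onward.

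The other variables covering these drugs are baseline ones: "Prescription during baseline period for systemic corticosteroids" and, for the conventional synthetic class, "Evidence of csDMARD prescribed within 180 days prior to index date". Section 8.7 announces frequencies for complications, hospitalization and mortality. It does not name the three drug-use endpoints and describes no division of their window. Section 8.3 leaves further definition to a SAP, which is not among the documents shown.

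**The concern.** Use of an immunosuppressant before influenza and use after it answer different questions. The first describes the patient's state when infected. The second describes what was prescribed or continued once the infection was recognised. A single indicator covering both answers neither.

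The mixing matters most for corticosteroids, because a course may be started for the acute respiratory illness. Section 8.2.1 says the database holds drugs both ordered and given, from inpatient and ambulatory systems, so a corticosteroid given during an influenza admission could set the indicator. Section 8.9 adds that milder cases tend to be under-recorded, so the captured cases may lean towards those in which treatment after diagnosis is more likely.

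Nothing in the documents suggests that methotrexate or azathioprine is given because of influenza. For them the loss is narrower: earlier use cannot be told from use that continued, resumed or began afterwards.

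In a descriptive study the frequency is itself the result. A reader who takes this one as the share of influenza cases immunosuppressed at infection would be reading in something the definition does not support.

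**Working it through.** **Window length.** 30 days before + the diagnosis day + 30 days after = 61 days. A patient whose only record is on day -20 and one whose only record is on day +5 are classified alike.

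**Can another listed variable separate them?**

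| Variable (Section 8.3) | Anchor | Direction |
|---|---|---|
| Corticosteroid, methotrexate, azathioprine use (secondary endpoints) | Influenza diagnosis | Both sides, [-30,30] |
| Pneumonia, stroke/MI, neurological disorder | Influenza diagnosis | On or after only |
| Hospitalization; death | Influenza diagnosis | After only |
| Baseline corticosteroid use | Index therapy date | Before index |
| Baseline csDMARD | Index therapy date | 180 days before index |

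The baseline variables do not help. The study period in Section 8.1 runs from 1 June 2014 to 31 May 2019, so influenza may follow the index date by months or years. No listed drug variable other than the pooled ones is anchored to influenza.

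**What the pooled figure hides.** The plan states no frequency for these endpoints, so there is nothing to reproduce. Let p be the share of influenza cases with use in [-30,-1], and q the share of the remaining cases with use in [0,+30]. The pooled share is

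U = p + (1 - p) × q.

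One value of U fits many pairs. All of these give 40%:

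- p = 40%, q = 0: 0.40 + 0.60 × 0 = 0.40
- p = 25%, q = 20%: 0.25 + 0.75 × 0.20 = 0.40
- p = 0, q = 40%: 0 + 1 × 0.40 = 0.40

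**Illustration for corticosteroids (p and q are assumptions, not taken from the documents).** With p = 25%:

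- q = 10%: U = 0.25 + 0.75 × 0.10 = 0.325; 0.325/0.25 = 1.30
- q = 20%: U = 0.25 + 0.75 × 0.20 = 0.40; 0.40/0.25 = 1.60

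A reader who took U as prior use would then overstate it by 30% to 60% in relative terms. With q near zero there would be almost no overstatement.

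**The case against.** The strongest reply is that nothing in the visible text says these variables are meant to show exposure at infection. They are defined as use around the diagnosis, and since neighbouring outcomes have forward windows, the two-sided one looks deliberate. Part of the objectives is not shown. This stands to the extent that no stated aim is demonstrably missed. It does not make the pooled frequency interpretable, because the documents attach no meaning to it that the mixture would serve.

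A second reply is that Section 8.3 defers definitions to the SAP. For these rows, however, the protocol has already stated the time period, so the point concerns a stated choice. The unseen SAP may already split the window. What counts as use (order date, supply or administration) is properly SAP content and is not faulted here.

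Three stronger readings are tempting, but the documents do not support them.

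- A reader might infer that all three indicators are contaminated by treatment given because of influenza. That is plausible for corticosteroids only.
- A reader might infer that long prescriptions cause methotrexate and azathioprine users to be missed. That depends on how use is defined, which is left to the SAP. The caveat in Section 8.9, "Information on prescriptions for outpatients does not necessarily indicate that the medication was consumed or taken as prescribed", concerns whether a drug was taken, not its timing relative to influenza.
- A reader might infer that, because early death shortens the forward window, the analysis should be confined to patients observed to day 30. That would remove early deaths, which are among the most severe cases.

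**Conclusion.** The point holds as a modest one. As written, the three frequencies cannot be read as immunosuppression at infection or as treatment after it, and no other listed variable supplies the distinction. The concern is strongest for corticosteroids and narrower for methotrexate and azathioprine.

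The size cannot be computed from the documents; the 30-60% figure shows only what the assumed inputs imply. The conclusion assumes that the SAP does not already divide the window. It concerns the interpretation of descriptive secondary endpoints. The primary incidence rates of influenza and influenza-like illness are unaffected, and no hypothesis test is described that it could touch.

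**What to change.** For each of the three drugs, replace the single row with:

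1. use in [-30,-1];
2. use in [0,+30];
3. use in [-30,30], kept as the union of the two.

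For corticosteroids, add a row for use in [0,+30] among cases with no recorded use in [-30,-1]. Label it exactly that way, because whether such use is truly new depends on how the SAP defines use.

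Use all influenza cases as the denominator for rows 1 to 3. Alongside them, state how many cases died or left observation before day 30, and do not exclude those cases. If the SAP already makes this split, a line in Section 8.3 saying so is enough.

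The cost is a few more table rows and smaller cells, which will be most noticeable once results are divided by indication, treatment and age. The existing window already requires dated records, so no new data are needed. Section 8.7 lets the SAP modify the plan and reserves protocol amendments for major changes to primary endpoint definitions or their analyses, so this change could be made in the SAP.
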